3.11.4 Arrhythmia Core Lab

An Arrhythmia Core Lab will oversee the provision, collection and analysis of data from the Event Monitors and Holter Monitors specified in this protocol.

- An Event Monitor will be provided at the 75-Day Remap to be used through the remainder of the 12-month follow-up interval for weekly scheduled and ad hoc symptomatic monitoring. Investigational sites will be provided with the Event Monitor and instructions for its use by the Arrhythmia Core Lab. The investigational sites will then provide the device and instructions for use to the subject. The Event Monitor will be returned to the Arrhythmia Core Lab at the time of the subject's exit from the study. ECG data from the Event Monitor will be analyzed by the Arrhythmia Core Lab.
- A 24-hour continuous ECG monitor will be provided at the 6 and 12-Month Visits. Investigational sites will be provided with the continuous ECG monitor device and instructions for its use by the Arrhythmia Core Lab. The investigational sites will then provide the device and instructions for use to the subject. The device will be worn by the subject for a single 24-hour period and

then returned to the Core Lab with shipping materials provided by the core lab. ECG data from this monitor will be analyzed by the Core Lab.

3.12 Schedule of Events and Assessments

Subjects will complete the following visits and assessments as indicated below and as summarized in **Section 3.12 Table 3 Summary of Study Assessments**.

3.12.1 Baseline

The following baseline data will be collected:

- Medical history
- AFD and anticoagulation medication history
- Pregnancy test (all women of child-bearing potential)
- 12-lead ECG
- Cardiac CT or MRI adequate to characterize left atrial and pulmonary vein dimensions
- TEE or other imaging modality for exclusion of left atrial thrombus
- NYHA Classification
- NIHSS score
- CHA₂DS₂-VASc score

3.12.2 Index Procedure

The Index Procedure will be performed according to **Section 3.11.1, Index Procedure**. The following procedural data will be collected:

- Pregnancy test (all women of childbearing potential if baseline pregnancy test obtained more than 14 days prior to procedure)
- Post-ablation 3D electroanatomical maps
- Post-ablation fluoroscopic examination of diaphragm motion to assess phrenic nerve response
- Adverse Events
- Procedural times
- Lesion set data
- Device deficiencies and malfunctions

3.12.3 Pre-Discharge

Prior to hospital discharge the following data will be collected:

- Adverse Events
- Data regarding the use, changes in or discontinuation of anticoagulation, rate control and/or antiarrhythmic medications.
- Cardiac rhythm as determined by a 12-lead ECG
- Occurrence, date, indication and outcome of any cardioversion(s)
- At the investigator's discretion: a post-procedural mediastinal gadolinium-enhanced MRI
- Stroke/TIA assessments

- NIHSS score
- A neurologic examination will be performed and recorded if:
 - If the NIHSS score has increased by 2 or more points
 - If there is a clinical suspicion of stroke or TIA

3.12.4 30-Day Visit

Discharged subjects will return for an office visit 30 days (\pm 7 days) post-ablation treatment. (Any subject who continues to be hospitalized 30 days post-ablation will have their 30-Day Visit assessment performed in-hospital). The following data will be collected at the 30-Day Visit:

- Adverse Events
- Symptoms of recurrent arrhythmia
- Data regarding the use, changes in or discontinuation of anticoagulation, rate control and/or antiarrhythmic medications.
- Cardiac rhythm as determined by a 12-lead ECG at the time of the visit
- Cardioversions, ablations or hospital admissions since last visit
- Heart failure status as assessed by NYHA classification at the time of visit

3.12.5 75-Day Visit and Remapping Procedure

Patients undergoing protocol-specified remapping:

Subjects will undergo the protocol-stipulated remapping procedure at 75 ± 15 days post-Index Procedure as defined in **Section 3.11.2, 75-Day Remap Procedure**.

- A 3D electroanatomical remapping procedure will be performed to assess electrical isolation of the pulmonary veins. Any electrical gaps may be closed at the investigator's discretion using study devices, or if necessary, a commercially approved ablation device (which constitutes a Therapeutic Failure).
- For patients who received extra-PV ablation at index, including those receiving ablation of the CTI, the persistence of nonconductivity in targeted tissue will be evaluated with either pacing maneuvers or electroanatomical mapping.

Procedure-specific data will be collected as follows:

- Procedural times
- Lesion set data
- Device deficiencies and malfunctions

All subjects whether undergoing remapping or not:

- Event Monitor: An Event Monitor and training will be provided to the subject, to be used for weekly scheduled and ad hoc symptomatic monitoring through the remainder of study follow-up. (**See Section 3.11.4, Arrhythmia Core Lab**). If necessary patients will be provided with an Event Monitor by mail, telephonic training and successful transmission of a monitoring record.
- AFD Management: For patients who do not require reablation during the 75-Day remap visit AFD may be stopped at the investigator's discretion.

The following data will be collected from all subjects at 75 ± 15 days:

- Adverse Events
- Symptoms of recurrent arrhythmia
- Fluoroscopic examination of diaphragm motion is required if:
 - Patient underwent remapping to assess phrenic nerve response
 - The patient declined a remap procedure but the post Index Procedure fluoroscopic examination indicated diminished phrenic nerve response
- Data regarding the use, changes in or discontinuation of anticoagulation, rate control and/or antiarrhythmic medications.
- Pregnancy test (all women of child-bearing potential) prior to remap
- Cardiac rhythm as determined by a 12-lead ECG
- Cardiac CT or MRI scan to assess the patency of the pulmonary veins
- Cardioversions, ablations or hospital admissions since last visit
- Heart failure status as assessed by NYHA classification at the time of visit

3.12.6 6-Month Visit

Subjects will return for an office visit 6 months (180 days \pm 30 days) following the Index Procedure. The following data will be collected at the 6-Month Visit:

- Adverse Events
- Symptoms of recurrent arrhythmia
- If either the post-Index Procedure or post-75-Day Remap Procedure fluoroscopies indicated diminished phrenic nerve response, and resolution has not been previously demonstrated, a repeat fluoroscopic examination. Females of childbearing potential undergoing this examination will also receive a pregnancy test prior.
- Data regarding the use, changes in or discontinuation of anticoagulation, rate control and/or antiarrhythmic medications
- Cardiac rhythm as determined by a 12-lead ECG at the time of the visit
- Arrhythmia assessment (See **Section 3.11.4, Arrhythmia Core Lab**).
 - A 24-hour continuous ECG monitor and training will be provided to the subject
 - Event Monitor compliance will be reviewed for weekly scheduled and ad hoc symptomatic monitoring and retraining of the subject provided as needed
- Cardioversions, ablations or hospital admissions since last visit
- Heart failure status as assessed by NYHA classification at the time of visit

3.12.7 12-Month Visit

Subjects will return for an office visit 12 months (365 days \pm 30 days) following the Index Procedure. At a minimum, the following data will be collected at the 12-Month Visit:

- Adverse Events

- Symptoms of recurrent arrhythmia
- If either the post-Index Procedure or post-75-Day Remap Procedure fluoroscopies indicated diminished phrenic nerve response, and resolution has not been previously demonstrated, a repeat fluoroscopic examination. Females of childbearing potential undergoing this examination will also receive a pregnancy test prior.
- Data regarding the use, changes in or discontinuation of anticoagulation, rate control and/or antiarrhythmic medications.
- Cardiac rhythm as determined by a 12-lead ECG at the time of the visit
- Arrhythmia assessment (See **Section 3.11.4, Arrhythmia Core Lab**).
 - A 24-hour continuous ECG monitor will be provided to the subject.
 - Instructions for returning the Event Monitor will be provided
- Cardioversions, ablations or hospital admissions since last visit
- Heart failure status as assessed by NYHA classification at the time of visit

3.12.8 Unscheduled Visits

Any unscheduled follow-up visits that occur throughout the study, other than routine follow-up visits per the institution's or investigator's normal standard of care, shall be documented. At the minimum, the following data will be collected:

- Adverse Events
- Symptoms of recurrent arrhythmia
- Cardiac rhythm as determined by a 12-lead ECG at the time of the visit
- Event Monitor compliance will be reviewed for weekly scheduled and ad hoc symptomatic monitoring and retraining of the subject provided as needed.
- Cardioversions, ablations or hospital admissions since last visit
- Heart failure status as assessed by NYHA classification at the time of visit

3.13 Schedule of Study Assessments

Table 3. Summary of Study Assessments

Assessment	Baseline	Procedure	Pre-Discharge	30-Days Post-Procedure (± 7 days)	75-Days (± 15 days)	6-Month (180 ± 30 days)	12-Month (365 ± 30 days)	Unscheduled
Medical History, CHA ₂ DS ₂ -VASC	X							
AFD and Anticoagulant Medications	X		X	X	X	X	X	X
Symptoms of recurrent arrhythmia				X	X	X	X	X
History of cardioversions, ablations, hospital admissions since last visit			X	X	X	X	X	X
Pregnancy test (for females of childbearing potential)	X	X			X	X ⁴	X ⁴	
12-lead ECG	X		X	X	X	X	X	X
24-Hour Continuous ECG Monitor (e.g., Holter)						X	X	
Cardiac CT/MRI for LA and PV dimensions	X				X			
Mediastinal MRI			X ¹					
TEE or other imaging modality (to exclude left atrial thrombus)	X							
Electroanatomical Mapping		X			X			
Event Monitor readiness/compliance					X	X	X	X
NIHSS	X		X					
Neurologic exam			X ²					
NYHA Classification	X		X	X	X	X	X	X
Fluoroscopic Examination of Diaphragm		X			X if remapped, X ³ if not	X ³	X ³	
Adverse Events		X	X	X	X	X	X	X

¹ At investigator's discretion

² If NIHSS score has increased by 2 or more points or if clinical suspicion of stroke/TIA

³ If the Index Procedure or Remap Procedure study indicated decreased phrenic nerve function and resolution has not yet been demonstrated.

⁴ As required for females of childbearing potential undergoing fluoroscopic examination of the diaphragm

4. Benefit Risk Assessment

The Sponsor has conducted an analysis of the benefits and risks of the FARAPULSE Endocardial Multi Ablation System and ablation procedure as described below. The conclusion of this review is that the subject investigation is justified because the overall potential benefit to the population outweighs the risks.

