6.1 Primary Safety Endpoint

The primary safety endpoint for this study is the Composite Safety Endpoint (CSE) defined as the incidence of the following early-onset and late-onset serious adverse events (SAEs) which are device- or procedure-related, as adjudicated by the CEDMC and defined below in **Table 4. Composite Safety Endpoint Definitions**.

Early onset (within 30 days of an Index or Remap Procedure)

- Death
- Myocardial infarction (MI)
- Persistent diaphragmatic paralysis
- Stroke or transient ischemic attack (TIA)
- Peripheral or organ thromboembolism
- Pericarditis
- Cardiac tamponade / perforation
- Vascular access complications requiring intervention
- Heart block

Late onset (any time during follow-up through 12 months)

- Pulmonary vein (PV) stenosis (> 70% diameter reduction from baseline)
- Atrio-esophageal fistula

Table 4. Composite Safety Endpoint Definitions

Adverse Event	Description/Criteria
Death	Death
Myocardial infarction (MI)	Myocardial infarction will be demonstrated by any one of the following: 1) detection of ECG changes indicative of new ischemia (new ST-T wave changes or new LBB) that persist for more than 1 hour. 2) development of new pathological Q waves on an ECG 3) imaging evidence of new loss of viable myocardium or new regional wall motion abnormality
Persistent diaphragmatic paralysis	Diaphragmatic paralysis: Change from baseline diaphragmatic function as demonstrated radiographically by elevation of the diaphragm above the normal range but not due to a pulmonary process such as atelectasis. Permanent: not resolved by completion of study follow-up
Stroke or transient ischemic attack (TIA)	Stroke is an acute symptomatic episode of neurological dysfunction attributed to a vascular cause (ischemia or hemorrhage) in which symptoms last more than 24 hours, or if symptoms last less than 24 hours, a brain imaging study demonstrates infarction. Transient ischemic attack is a new focal neurological deficit with rapid symptom resolution always within 24 hours.

Adverse Event	Description/Criteria
Peripheral or organ thromboembolism	Formation in a blood vessel of a clot (thrombus) that results from the breaking loose of all or part of an existing thrombus, which is then carried by the blood to lodge in/occlude a more distal vascular site.

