Pericarditis	Inflammation of the pericardial space that results in an effusion that leads to hemodynamic compromise or required pericardiocentesis, prolongs hospitalization by more than 48 hours, requires hospitalization, or persists for more than 30 days following the ablation procedure.
Cardiac tamponade/perforation	The development of a significant pericardial effusion during or within 30 days of undergoing the index AF ablation procedure. A significant pericardial effusion is one which results in hemodynamic compromised (<80mmHg systolic bp), requires elective or urgent pericardiocentesis, or results in a 1cm or more pericardial effusion as documented by echocardiography.
Vascular access complications requiring intervention	Vascular access complication (e.g. groin hematoma, AV fistula, pseudoaneurysm) requiring intervention (e.g. surgical repair, blood transfusion).
Heart block	Impairment of AV conduction requiring permanent pacing intervention, if resulting from inappropriate ablation application.
Pulmonary vein (PV) stenosis	>70% diameter reduction of pulmonary vein from baseline CT/MRA scan.
Atrio-esophageal fistula	Connection between the atrium and the lumen of the esophagus as evidenced by documentation of esophageal erosion combined with evidence of a fistulous connection to the atrium.

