COUNT of [(Left Superior Isolated/Blocked ='Yes', Left Inferior Isolated/Blocked='Yes', Left Common Ostium Isolated/Blocked='Yes', Right Middle Isolated/Blocked='Yes', Right Superior Isolated/Blocked='Yes', Right Inferior Isolated/Blocked='Yes')] / COUNT of [(Left Superior Isolated/Blocked in (Yes, No) , Left Inferior Isolated/Blocked in (Yes, No), Left Common Ostium Isolated/Blocked in (Yes, No), Right Middle Isolated/Blocked in (Yes, No), Right Superior Isolated/Blocked in (Yes, No), Right Inferior Isolated/Blocked in (Yes, No))] **in Procedural data form (PR)**
- Derived criteria "Proportion of all ablated pulmonary veins isolated using the study device during the Index Procedure that remain isolated at the 75-day remapping procedure" will be defined as follows:
(Derived criteria "Total number of veins isolated" - Derived criteria "Number of veins with gaps")/ Derived criteria "Total number of veins isolated"
- Derived criteria Proportion "Chronic CTI at 75d remap" will be defined as follows:
IF CTI lesion durable ='Yes' **in Follow-up 3D electroanatomical mapping form (RM)** **THEN** Chronic CTI at 75d remap ='Yes'
ELSE IF CTI lesion durable ='No' **in Follow-up 3D electroanatomical mapping form (RM)** **THEN** Chronic CTI at 75d remap ='No'
- Derived criteria Proportion "LAPW chronic isolation" will be defined as follows:
IF Anatomical Structure/Area other specification 1 **IN** ("POSTERIOR WALL" "LA POSTERIOR WALL" "LAPW" "PA WALL" "BOX POSTERIOR WALL") **AND** Other 1 Lesion durable = 'yes' **OR** Anatomical Structure/Area other specification 2 **IN** ("POSTERIOR WALL" "LA POSTERIOR WALL" "LAPW" "PA WALL" "BOX POSTERIOR WALL") **AND** Other 2 Lesion durable = ='Yes' **in Follow-up 3D electroanatomical mapping form (RM)** **THEN** LAPW chronic isolation= 'Yes'

CONFIDENTIEL / CONFIDENTIAL

Toute reproduction ou distribution, totale ou partielle, de ce document, sans autorisation préalable de ICON PLC est interdite.
Reproduction and distribution of this document, in whole or in part, is strictly forbidden without prior authorization from ICON PLC.

	STATISTICAL ANALYSIS PLAN	FARAPULSE PersAFOne SAP V1.0 PERSAFONE Page 26 /49
---	----------------------------------	--

ELSE LAPW chronic isolation = 'No'

Primary Safety endpoint

Unless otherwise indicated, all the following variables will be derived from the Adverse event adjudication form (CE)

- Derived criteria "Death" will be defined as follows:

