IF (30≤ (EVENT DATE-PROCEDURE DATE IN **PROCEDURAL DATA FORM (PR)**) **OR** (30≤ (EVENT DATE-≤REMAPPING DATE IN **FOLLOW-UP 3D ELECTROANATOMICAL MAPPING FORM (RM)**) **AND** PRIMARY SAFETY ENDPOINT EVENT CRITERIA=' Death' **THEN** DEATH='Yes'
ELSE DEATH='No'

- Derived criteria "Myocardial infarction" will be defined as follows:

IF (30≤ (EVENT DATE-PROCEDURE DATE IN **PROCEDURAL DATA FORM (PR)**) **OR** (30≤ (EVENT DATE-REMAPPING DATE IN **FOLLOW-UP 3D ELECTROANATOMICAL MAPPING FORM (RM)**) **AND** PRIMARY SAFETY ENDPOINT EVENT CRITERIA=' Myocardial infarction' **THEN** Myocardial infarction='Yes'.

ELSE Myocardial infarction ='No'.

- Derived criteria "PV Stenosis" will be defined as follows:

IF (0≤ (EVENT DATE-PROCEDURE DATE IN **PROCEDURAL DATA FORM (PR)**) ≤360 **AND** PRIMARY SAFETY ENDPOINT EVENT CRITERIA=' PV Stenosis' **THEN** PV Stenosis ='Yes'.
ELSE PV Stenosis ='No'.

- Derived criteria "Diaphragmatic Paralysis" will be defined as follows:

IF (30≤ (EVENT DATE-PROCEDURE DATE IN **PROCEDURAL DATA FORM (PR)**) **OR** (30≤ (EVENT DATE-REMAPPING DATE IN **FOLLOW-UP 3D ELECTROANATOMICAL MAPPING FORM (RM)**) **AND** PRIMARY SAFETY ENDPOINT EVENT CRITERIA=' Diaphragmatic Paralysis' **THEN** Diaphragmatic Paralysis ='Yes'.
ELSE Diaphragmatic Paralysis ='No'.

- Derived criteria "AE fistula" will be defined as follows:

IF (0≤ (EVENT DATE-PROCEDURE DATE IN **PROCEDURAL DATA FORM (PR)**) ≤360 **AND** PRIMARY SAFETY ENDPOINT EVENT CRITERIA=' AE fistula' **THEN** AE fistula ='Yes'.
ELSE AE fistula ='No'.

- Derived criteria "TIA" will be defined as follows:

IF (30≤ (EVENT DATE-PROCEDURE DATE IN **PROCEDURAL DATA FORM (PR)**) **OR** (30≤ (EVENT DATE-REMAPPING DATE IN **FOLLOW-UP 3D ELECTROANATOMICAL MAPPING FORM (RM)**) **AND** PRIMARY SAFETY ENDPOINT EVENT CRITERIA=' TIA' **THEN** TIA=Yes.
ELSE TIA='No'.

- Derived criteria "CVA" will be defined as follows:

CONFIDENTIEL / CONFIDENTIAL

Toute reproduction ou distribution, totale ou partielle, de ce document, sans autorisation préalable de ICON PLC est interdite.
Reproduction and distribution of this document, in whole or in part, is strictly forbidden without prior authorization from ICON PLC.

	STATISTICAL ANALYSIS PLAN	FARAPULSE PersAFOne SAP V1.0 PERSAFONE Page 27 /49
---	----------------------------------	--

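### PV stenosis is tabulated as a 12-month rate on all ITT subjects, although the only scheduled follow-up scan is at 75 days and a subject without one is coded 'No'

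*Protocol*

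**What the plan says.** **Endpoint.** Protocol 6.1 places PV stenosis under "Late onset (any time during follow-up through 12 months" in the Composite Safety Endpoint. The composite is the incidence of device- or procedure-related serious adverse events adjudicated by the CEDMC. Protocol Table 4 gives the criterion for this component: ">70% diameter reduction of pulmonary vein from baseline CT/MRA scan".

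**Imaging.** Protocol Table 3 schedules "Cardiac CT/MRI for LA and PV dimensions" at baseline and at 75 ± 15 days. The 6-month, 12-month and unscheduled columns are blank. Section 3.12.5 lists "Cardiac CT or MRI scan to assess the patency of the pulmonary veins" among the data collected from all subjects at that visit, remapped or not. Section 3.12.7 opens its list with "At a minimum, the following data will be collected at the 12-Month Visit", and the list contains no PV imaging.

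**Re-ablation.** Sections 3.11.3 and 3.12.5 allow re-ablation at the remap or at another procedure in the Blanking Period. No PV scan is scheduled after the 75-day visit.

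**Derivation.** SAP 2.5 introduces the safety variables with "Unless otherwise indicated, all the following variables will be derived from the Adverse event adjudication form (CE". The stenosis rule returns 'Yes' when the event falls between day 0 and the cut-off and carries the matching criterion ("≤360 AND PRIMARY SAFETY ENDPOINT EVENT CRITERIA=' PV Stenosis"). Every other subject receives "PV Stenosis ='No".

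**Reporting.** SAP 2.4.8 sets the safety analysis on ITT. SAP Table 8 shows n/N with a 95% interval for PV stenosis beneath a 12-month subtotal.

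**The concern.** A diameter criterion relative to baseline can be assessed only where a second scan exists. The derivation never asks whether one does. It reads the adjudication form and, finding no stenosis there, records 'No'. A subject scanned and clear, a subject who missed the scan and a subject who left the study before day 75 all contribute the same favourable value to the same denominator.

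The heading adds a second difficulty. Detection is systematic up to one scan at about day 75 and clinically prompted after it, and Table 8 presents the mixture as one 12-month rate. Veins re-ablated after that scan have no later scheduled imaging, so for them no scan on the schedule reflects the final lesion set.

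This sits in the primary safety endpoint of a study whose results are meant to inform later studies (Protocol 5.3). A reader planning one of those could take the row as a 12-month imaging result, with no planned table showing how many subjects were scanned.

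**Working it through.** The documents give no expected stenosis rate and no sample size calculation, so there is no stated figure to reproduce. The check traces the rule and then sizes its effect.

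**1. Does any rule elsewhere repair the 'No'?**
- Protocol 5.5 and SAP 2.1.2 say missing data are not replaced. The ELSE branch in effect replaces a missing assessment with 'No'.
- SAP 2.5 opens with a general rule that a derived criterion is missing if an item it needs is missing. Scan status is not an input to the stenosis rule, so an absent scan does not trigger it. Applied literally to the event date, it would make every event-free subject missing.
- SAP Table 6 uses remapped veins as its denominator and has a row for missing data. No equivalent is planned for PV scans.

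**2. Follow-up without scheduled PV imaging**, (365 − scan day)/365:

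| Scan day | Days remaining | Share of 365 |
|---|---|---|
| 60 | 305 | 84% |
| 75 | 290 | 79% |
| 90 | 275 | 75% |

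**3. Size of the denominator effect.** Inputs:
- N = 40, the planned maximum (Protocol 3.7).
- Scan completion is not given. As an assumption, use remap attendance in the two earlier sponsor studies: 35/40 = 87.5% (Protocol 1.3.1) and 49/60 = 81.7% (Protocol 1.3.2). Applied to 40, these give 35 and 32.7, taken as 33.
- Interval: SAP 2.1.4 specifies Agresti-Coull when the asymptotic assumptions fail and the proportion is 0%.

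For x = 0 and z = 1.96: ñ = n + z², p̃ = (z²/2)/ñ, upper limit = p̃ + z√(p̃(1 − p̃)/ñ).

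| n | ñ | p̃ | z × SE | Upper limit |
|---|---|---|---|---|
| 40 | 43.84 | 0.0438 | 0.0606 | 10.4% |
| 35 | 38.84 | 0.0495 | 0.0682 | 11.8% |
| 33 | 36.84 | 0.0521 | 0.0718 | 12.4% |

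Subtracting the rounded limits gives 1.4 and 2.0 points (1.3 and 2.0 before rounding). Exact Clopper-Pearson limits for the same counts are 8.8%, 10.0% and 10.6%. With one event the point estimate moves from 1/40 = 2.5% to 1/35 = 2.9% or 1/33 = 3.0%.

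**4. Size of the label effect.** This depends on how many stenoses arise or progress after the scan and how many of those come to clinical attention. The documents give neither, so it is not quantified.

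**5. Related detail.** The SAP cut-off is day 360, while the 12-month visit spans 365 ± 30, that is days 335 to 395. A stenosis found at that visit and dated after day 360 would be coded 'No' in a row headed as 12-month.

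**The case against.** The strongest reply is that the endpoint counts adjudicated serious adverse events, not stenoses on paired scans. Adverse events are collected at every visit to 12 months, so a stenosis found clinically after day 75 still counts (up to the SAP's day 360), and the heading correctly names the event window. ITT with 'No' as default is also the SAP's rule for the other components. This stands for the composite, and it is why the composite should not change. It does not answer the point about the component row, whose criterion needs a scan.

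Three stronger readings are tempting but unsupported:
- *That many subjects will be un-scanned.* The 75-day scan is required of all subjects. Completion is unknown, and remap attendance is only a proxy. A missed scan should also surface as a protocol deviation (SAP 2.3.2), although the deviation tables do not supply a denominator for stenosis.
- *That every re-ablated vein escapes imaging.* Protocol 3.11.3 allows repeat ablation outside the remap, so one done before the scan would be covered. The order of scan and remap within the visit window is not stated. The earlier studies' reconnection counts (21/35 and 10/49) cannot be turned into a number re-ablated here, because closing gaps is discretionary.
- *That un-imaged subjects should simply be set to missing throughout.* PV stenosis feeds the total composite in SAP 2.5. Under the general missing-item rule, a missing component could make the composite missing. A subject who died or had tamponade before day 75 could then drop out of the primary safety count.

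It is also fair that the study is descriptive and that the numerical effect is small.

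**Conclusion.** The point holds as a reporting defect in one row of the primary safety table. An imaging-defined component with one scheduled follow-up scan is presented as a 12-month rate on all ITT subjects, and the coding hides who was scanned. With zero events at N = 40, restricting to scanned subjects raises the upper limit by about 1.4 to 2.0 points, assuming 82% to 88% scan completion. If all subjects are scanned, that difference is nil. The labelling problem does not depend on that assumption: even with complete scanning, 75% to 84% of the year has no scheduled PV imaging. The documents do not support saying that the composite is invalid or that stenoses will be missed in any stated number.

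**What to change.** 1. Leave the Composite Safety Endpoint and its ITT denominator as they are. State in SAP 2.5 that a subject with any other component event still counts, and that missing scan status does not make the composite missing.
2. In SAP Table 8, report the component as PV stenosis at 75-day imaging, with subjects who have both a baseline and a follow-up CT/MRI as denominator. Show the number without paired scans as missing.
3. List separately any stenosis detected clinically after that scan through 12 months, and align the day-360 cut-off with whatever window the heading names.
4. State how many subjects were re-ablated after their last PV scan.

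No imaging is added and care does not change. Protocol 5.2 has PV dimensions read by third parties, so paired-scan status should be obtainable. The cost is a change to SAP and table wording, and a slightly wider interval for this row.
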